6.3. Other Endpoints

6.3.1. Additional Plasma PF-07293893 Parameters

Additional PK parameters detailed in Section 3.3.1 will be listed and summarized for participants in the PK Parameter Analysis Set (as defined in Section 4). Missing values will be handled as detailed in Section 5.3.2 and 5.3.3. Each PK parameter will be summarized by dose (and formulation and fasting condition, if appropriate) as applicable. Each summary will include the set of summary statistics as specified in Table 5.

Table 5. Summary Statistics for Additional PF-07293893 Plasma PK Parameters

Parameter	Summary Statistics
CL/F*, V_z/F^* , $AUC_{last}(dn)$, $AUC_{inf}(dn)^*$, $C_{max}(dn)$	N, arithmetic mean, median, cv%, standard deviation, minimum, maximum, geometric mean and geometric cv%.

*If data permit

Box and whisker plots for dose-normalized PK parameters [AUC_{inf} (dn), AUC_{last} (dn) and C_{max} (dn)] will be presented in logarithmic scale by dose and treatment (if applicable) and overlaid with observed values of individual participants and geometric means. Geometric means will have a different symbol than the individual values. Individual values from different cohorts will also have a different symbol. A footnote will be added to the plots to indicate that geometric means are presented and that data from all cohorts are presented on the plot.

The nominal PK sampling time will be used for summary statistics and relevant plots.

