2.2.4. Biopharmaceutics

PF-07293893 is a neutral compound. CCl [REDACTED] and apparent permeability, as measured in cell lines, indicate that the molecule should readily CCl [REDACTED] membrane. The solubility of the crystalline form will be CCl [REDACTED] in gastric fluid and in the intestinal pH. Based on preclinical exposure data and *in silico* modelling, the PF-07293893 crystalline form is expected to be CCl [REDACTED] absorbed under fasted condition CCl [REDACTED] mg, and CCl [REDACTED] absorbed at the dose range CCl [REDACTED] mg in the FIH study using a suspension formulation. Based on physiochemical properties and *in silico* predictions, food is expected to CCl [REDACTED] exposure of crystalline PF-07293893.

A SDD is predicted to have an CCl [REDACTED] PK profile as compared to the crystalline form by CCl [REDACTED] exposure over the entire dose range. The solubility of the SDD will be CCl [REDACTED] in gastric fluid and in the intestinal pH. PF-07293893 SDD is expected to be CCl [REDACTED] absorbed under fasted condition at the predicted dosing range CCl [REDACTED] mg, and CCl [REDACTED] absorbed at the dose range CCl [REDACTED] mg in the FIH study using a suspension formulation.

Based on available physiochemical, preclinical PK and *in silico* oral absorption data it is anticipated that dose limiting absorption may occur in the dose range CCl [REDACTED] mg for crystalline form and CCl [REDACTED] mg for SDD due to solubility limitations. Consequently, C_{max} and/or AUC may decrease at higher doses.

Data on the human exposure from SDD versus crystalline PF-07293893 will be used to optimize the performance of the drug product.

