4.2. Scientific Rationale for Study Design

The population planned for this study will be healthy male and female participants. Female participants will be confirmed to be of non-childbearing potential, since at the present time embryo-fetal developmental toxicity studies with PF-07293893 have not been conducted. In male participants, appropriate measures are expected to be followed to minimize potential transfer of PF-07293893 via semen to partners (see [Appendix 4](#)).

Given this is the first time PF-07293893 will be administered to humans, an escalating single oral dose crossover design with careful assessment and ongoing review of safety, tolerability and PK data of PF-07293893 is planned. Due to the findings of transient clinical signs of cardiovascular and neuropulmonary effects in the non-clinical chronic toxicology studies, neurological examination, RR and body temperature measurement will be performed in this study. In addition, a precautionary sentinel dosing will be used. The highest anticipated C_{max} and AUC_{24} of PF-07293893 will not exceed the pre-defined human exposure stopping limits. Furthermore, to permit an unbiased assessment of safety, the participants' treatment assignments (active treatment versus placebo) will be blinded to both site staff (except those involved in preparation of doses) as well as the study participants. However, to permit real-time review of the safety and PK data, a limited number of sponsor study team members will be unblinded (see [Section 6.4.3](#)).

In each period, approximately 6 participants are planned to receive PF-07293893, and 2 participants are planned to receive placebo. The 4-period crossover design will permit both within and between participant assessment of safety/tolerability and PK at multiple dose levels and placebo. An additional cohort may be included if, based on emerging data from the first 2 cohorts, it is deemed necessary to meet the objectives of this study. For a given participant, dosing will be separated by at least 7 days. This planned dosing interval is deemed sufficient based on the projected PF-07293893 terminal half-life (see [Section 4.3.1](#)).

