9.3.2.2. Statistical Methods for PK Data

Plasma concentrations of PF-07293893 will be listed and summarized descriptively by dose (formulation and fasting condition, if appropriate) and nominal PK sampling time. Individual participant and median profiles of the plasma concentration-time data will be plotted by dose (formulation and fasting condition, if appropriate) using actual (for individual) and nominal (for median) times respectively. Median profiles will be presented on both linear and log scales.

The plasma PK parameters will be summarized descriptively by dose (formulation and fasting condition, if appropriate) as applicable. Dose-normalized AUC_{inf}, AUC_{last}, and C_{max} will be plotted against dose (formulation and fasting condition, if appropriate) using a logarithmic scale, and will include individual participant values and the geometric means for each dose. These plots will be used to understand the relationship between the PK parameters and dose (formulation and fasting condition, if appropriate).

If the formulation and/or food effect is assessed, a mixed effects ANOVA will be performed separately on the natural log transformed AUC_{inf}, AUC_{last}, and C_{max} (dose-normalized prior to analysis, if appropriate) with formulation and/or fasting condition included as a fixed effect and participant as a random effect. Further details of this analysis will be provided in the SAP, where modifications to the model may be outlined depending on dosing schema implemented.

Additional PK analyses may be performed if deemed appropriate and may not be included in the CSR.

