3.2. Secondary Endpoint(s)

Blood samples for PK analysis of PF-07293893 will be taken according to the SoA in the protocol. *The plasma PK parameters for PF-07293893, following oral dose administration, will be derived from the plasma concentration-time profiles using standard noncompartmental methods as detailed in Table 2, as data permit.* Table 2 also shows the analysis scale and method for each parameter.

In all cases, actual PK sampling times will be used in the derivation of PK parameters. If actual PK sampling times are not available, nominal PK sampling times will be used in the derivation of PK parameters.

The following plasma PK parameters as described in Table 2 will be determined.

Table 2. Plasma PF-07293893 PK Parameters

Parameter	Definition	Method of Determination	Analysis Scale	PF-07293893
AUC_{last}	Area under the plasma concentration-time profile from time 0 to the time of the last quantifiable concentration (C_{last})	Linear/Log trapezoidal method	ln	D, A
AUC_{inf}^*	Area under the plasma concentration-time profile from time 0 extrapolated to infinite time	$AUC_{last} + (C_{last}^* / kel)$, where C_{last}^* is the predicted plasma concentration at the last quantifiable timepoint estimated from the log-linear regression analysis	ln	D, A

C_{max}	Maximum plasma concentration	Observed directly from data	ln	D, A
T_{max}	Time for C_{max}	Observed directly from data as time of first occurrence	R	D
$t_{1/2}^*$	Terminal elimination half-life	$\log_e(2)/kel$, where kel is the terminal phase rate constant calculated by a linear regression of the log-linear concentration-time curve. Only those data points judged to describe the terminal log-linear decline will be used in the regression.	R	D

Key: ln=natural-log transformed, R=raw (untransformed),
 D=displayed with descriptive statistics,
 A=analysed using a statistical model (for evaluating food effect)
 *=if data permit

T_{last} will also be provided as a support parameter for AUC_{last} . T_{last} values will only be listed and not summarized.

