3.3. Other Endpoint(s)

3.3.1. Additional Plasma PF-07293893 Parameters

Additional plasma PF-07296893 PK parameters, as described in Table 3, will be determined.

Table 3. Additional PF-07293893 PK Parameters

Parameter	Definition	Method of Determination	Analysis Scale	PF-07293893
CL/F^*	Apparent clearance	Dose/AUC_{inf}	ln	D
V_z/F^*	Apparent volume of distribution	Dose/($AUC_{inf} \times kel$)	ln	D
$AUC_{last}(dn)$	Dose-normalized AUC_{last}	$AUC_{last}/Dose$	ln	D
$AUC_{inf}(dn)^*$	Dose-normalized AUC_{inf}	$AUC_{inf}/Dose$	ln	D
$C_{max}(dn)$	Dose-normalized C_{max}	$C_{max}/Dose$	ln	D

Key: ln=natural-log transformed,
 D=displayed with descriptive statistics,
 *=if data permit

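### Exposure against dose is to be read from unlinked box plots, so the crossover's within-participant information goes unused and a chance cohort difference can look like non-proportional PK

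*SAP*

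**What the plan says.** Protocol 9.3.2.2 plans plots of dose-normalised AUCinf, AUClast and Cmax against dose and gives their purpose: "These plots will be used to understand the relationship between the PK parameters and dose". SAP 6.3.1 specifies them as box and whisker plots that "will be presented in logarithmic scale by dose and treatment (if applicable) and overlaid with observed values of individual participants and geometric means". It adds: "Individual values from different cohorts will also have a different symbol". Nothing joins one participant's values at different doses.

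In SAP Table 3 the dose-normalised parameters carry only the code "D=displayed with descriptive statistics". In SAP Table 2 the code for a statistical model is reserved for food effect. The mixed model in SAP 5.2.3, with its random participant effect, has the same scope. No slope, dose ratio or interval for exposure against dose is planned.

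Two other passages bear on this. Protocol 4.2 justifies the design by saying: "The 4-period crossover design will permit both within and between participant assessment of safety/tolerability and PK at multiple dose levels". Protocol 2.2.4 expects solubility to limit absorption at some point, so that Cmax and/or AUC "may decrease at higher doses".

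**The concern.** Most participants receive several active doses, so the trial contains direct within-person comparisons of dose-normalised exposure. A box plot by dose treats the values at each dose as a separate group. Its geometric means mix the dose effect with differences between the people who happened to be on active drug at that dose.

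This matters most where the plot passes from one cohort to the next, because the people then change completely. If that step falls towards the high doses, a chance cohort difference appears in the region where Protocol 2.2.4 expects exposure to fall short. The reader would have no interval by which to judge it.

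**Working it through.** **The plan's own figures.** Protocol 9.5: 3 cohorts × 8 = 24 participants. At 3:1, 8 × 3/4 = 6 active and 2 placebo per dose, as stated. The projections in Protocol Table 3 are proportional: Cmax 57.9/10 = 5.79 and 8684/1500 = 5.79 ng/mL per mg; AUC24 671/10 = 67.1 and 100600/1500 = 67.1 ng·h/mL per mg. No variability, slope or proportionality criterion is given in readable text.

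**Assumptions.** Log-normal, exactly proportional PK with variance ln(1 + CV²). Two cohorts of 8, six active per dose. Low/high split: 10, 30, 100, 300 mg in one cohort and 750, 1500 mg in the other. Interleaved alternative: 10, 100, 750 mg and 30, 300, 1500 mg. The CVs and both splits are assumed.

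**Step between cohorts (750:300 mg under the low/high split).** Six people are compared with six others, so SE = √[2(σb² + σw²)/6]. At CV 40/20%, σb² = ln 1.16 = 0.1484 and σw² = ln 1.04 = 0.0392. SE = √(0.1876/3) = 0.250, and the 95% chance limits are exp(1.96 × 0.250) = ×/÷1.63.

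| Between/within CV | SE (log) | 95% chance limits | Beyond 1.25-fold | Beyond 1.5-fold |
|---|---|---|---|---|
| 20/15% | 0.143 | ×/÷1.32 | 12% | under 1% |
| 30/15% | 0.190 | ×/÷1.45 | 24% | 3% |
| 40/20% | 0.250 | ×/÷1.63 | 37% | 10% |
| 50/25% | 0.308 | ×/÷1.83 | 47% | 19% |

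**Step within a cohort (1500:750 mg), CV 40/20%.** With different pairs on placebo, four people receive both doses and two receive only one of them at each dose. The raw ratio of geometric means has variance σw²/3 + σb²/9 = 0.0131 + 0.0165 = 0.0296, SE 0.172, limits ×/÷1.40. The four pairs alone give √(2σw²/4) = 0.140, or ×/÷1.32. A mixed model with dose as a category and a random participant effect (variances taken as known) also uses the unpaired values and gives ×/÷1.30.

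**The same model on the step between cohorts.** At CV 40/20% the limits move only from ×/÷1.63 to ×/÷1.57. Without a shared dose there is almost no within-person information to recover.

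**Slope of ln(parameter) on ln(dose), CV 40/20%.**

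| Split | SE, pooled | SE, random participant |
|---|---|---|
| Low/high | 0.048 | 0.030 |
| Interleaved | 0.032 | 0.021 |

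Under the low/high split, (0.048/0.030)² is about 2.6 times the information. Over four splits and five CV pairs the pooled SE was about 1.2 to 2.1 times the mixed-model SE. A fixed cohort term raises the low/high mixed-model SE to 0.033, still below pooled.

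**Can the slope show a plateau?** If exposure does not rise from 750 to 1500 mg, the dose-normalised value halves (750/1500 = 0.5). Under the low/high split at CV 40/20% this moves the mixed-model slope by only −0.045, which is 0.045/0.030 = 1.5 SE. The modelled 1500:750 ratio of 0.5 lies well below its lower chance limit of 1/1.30 = 0.77. The adjacent-dose ratio is the better tool for this question.

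**The case against.** The strongest reply is that this is an exploratory display in a first-in-human trial of 16 to 24 people. No objective names dose proportionality, the dose-normalised parameters are tertiary, and both documents rule out hypothesis testing. Dose escalation under Protocol 6.6.1 works from observed exposures and projections from them, not from this plot. PK parameters, including CL/F, are also summarised by dose; concentration-time plots by participant are planned; and Protocol 9.3.2.2 leaves room for further PK analyses. All of this stands and limits the weight of the point. It does not supply an estimate: the participant plots are not dose-normalised, and an open option is not a specified analysis.

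A reader might infer that the plot hides the cohort effect, so that a plateau and a cohort difference cannot be told apart. The documents do not support that. Cohorts have their own symbols, and under the low/high split a drop from 750 to 1500 mg occurs within one cohort, in mostly the same people.

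A reader might also take it as known that one cohort gets low doses and the other high doses. The allocation is in a figure that is not shown, and planned doses may be modified. Interleaving would reduce the imprecision of a pooled slope, as the working shows.

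Finally, a reader might expect a random participant effect to remove the confounding. It does not: the step between cohorts barely tightens.

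**Conclusion.** The point holds as a modest, inexpensive improvement to an exploratory analysis. The planned reading of exposure against dose is graphical, leaves each participant's values unlinked and carries no interval, so it does not use a comparison that the protocol gives as a reason for the crossover.

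If cohorts cover different dose ranges, a chance step beyond 1.25-fold under exact proportionality arises in about 12% to 47% of trials over the assumed CVs, and beyond 1.5-fold in under 1% to 19%. It can therefore look like non-proportionality, but need not. The gain from modelling is clear within a cohort (×/÷1.40 to ×/÷1.30 at CV 40/20%) and for the slope, and small between cohorts.

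These sizes rest on assumed CVs, assumed splits, known variances and two cohorts. Cohort 3 is left out, although SAP 6.2 uses its periods for the SDD food effect with fasted dosing as reference; if conducted, it would add fasted SDD data. No formal inference in the plan is wrong, because none is planned on this question.

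**What to change.** Add to SAP 6.3.1, for fasted SDD periods and as estimation only:

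1. On the dose-normalised plots, join each participant's points across doses and keep the cohort symbols.
2. Fit a mixed model to ln dose-normalised Cmax, AUClast and AUCinf, with dose as a categorical fixed effect and participant as a random effect (REML and Kenward-Roger, as in SAP 5.2.3). Report ratios between adjacent doses with 90% CIs, and mark which are within a cohort and which compare cohorts.
3. Fit a power model of ln(parameter) on ln(dose) with a random participant effect. Report the slope with its 90% CI as an overall summary.
4. State two limits: the slope alone can be insensitive to a plateau at the top dose, and cohort and dose remain partly confounded unless cohorts share a dose.

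The cost is a paragraph in the SAP, a few lines added to the Appendix 2 code and one extra table. No new data are needed. Because only estimates and intervals are reported, the statement that no hypothesis is tested still holds; the food-effect model already reports 90% CIs on that basis. The downside is somewhat more output for an exploratory question.

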6.3.2. Plasma PF-07293893 PK parameters during crystalline form period if conducted

If the formulation and/or food effects are assessed, the PK parameters described in Section 3.3.2 will also be summarized descriptively as described above in Section 6.2 by formulation and/or fasting condition.

To assess any food effect in crystalline formulation, a mixed effects model *will be performed separately on the natural log transformed AUC_{inf} , AUC_{last} , and C_{max} (dose-normalized prior to analysis, if appropriate)* with fasting condition *included as a fixed effect and participant as a random effect* as described in Section 5.2.3. If performed, only data from the respective periods that includes the crystalline formulation will be included. The fasted state will be the reference and the fed state will be the test treatment.

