9. STATISTICAL CONSIDERATIONS

Detailed methodology for summary and statistical analyses of the data collected in this study is outlined here and further detailed in the SAP, which will be maintained by the sponsor. The SAP may modify what is outlined in the protocol where appropriate; however, any major modifications of the primary endpoint definitions or their analyses will also be reflected in a protocol amendment.

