2.1. Modifications to the Analysis Plan Described in the Protocol

No modification.

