2.2. Study Objectives, Endpoints, and Estimands

Type	Objective	Endpoint
	Primary	Primary
Safety Section 6.1	
 To evaluate the safety and tolerability of single ascending doses of PF-07293893 administered orally to healthy adult participants. 	
 Assessment of adverse events, clinical safety laboratory tests, vital signs, continuous cardiac monitoring, 12-lead electrocardiograms, physical examinations and neurological examinations.
	Secondary	Secondary
PK Section 6.2	
 To evaluate the PK of PF-07293893 following single doses of PF-07293893 administered orally to healthy adult participants. 	
 PK parameters derived from plasma PF-07293893 concentrations: C_{max}, T_{max}, AUC_{last}, and if data permit, AUC_{inf}, and $t_{1/2}$.
	Tertiary/Exploratory	Tertiary/Exploratory
PK Section 6.3.1	
 To evaluate additional PK parameters of PF-07293893 following single doses of PF-07293893 administered orally to healthy adult participants. 	
 Additional PK parameters derived from plasma PF-07293893 concentrations: $C_{max}(dn)$, $AUC_{last}(dn)$ and if data permit, $AUC_{inf}(dn)$, CL/F and V_z/F.
PK Section 6.3.2	
 To evaluate the PK of PF-07293893 following single dose(s) of a crystalline and SDD form of PF-07293893 in fasted and/or fed state, if conducted. 	
 PK parameters derived from plasma PF-07293893 concentrations: C_{max}, T_{max}, AUC_{last}, and if data permit, AUC_{inf}, and $t_{1/2}$.
Biomarker Section 6.3.3	
 To evaluate the effects of single ascending doses of PF-07293893 on biomarker(s) of transporter activity, if feasible & analyzed. 	
 For each biomarker (as applicable): AUC_{24} and C_{max}

There are no estimands for this study.

[figure not shown]

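### The SAP leaves any crystalline-versus-SDD comparison descriptive, although the protocol foresees a formulation term in the model and SAP 2.1 declares no modification

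*SAP*

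**What the plan says.** **Protocol.** Section 4.2 allows an optional exploratory look at crystalline PK relative to SDD, and Section 2.2.4 says that human exposure data on the two forms will inform optimisation of the drug product. Section 9.3.2.2 gives the method: "If the formulation and/or food effect is assessed, a mixed effects ANOVA will be performed separately" on ln AUCinf, ln AUClast and ln Cmax (dose-normalised where appropriate), "with formulation and/or fasting condition included as a fixed effect and participant as a random effect". The same section sends details to the SAP, "where modifications to the model may be outlined depending on dosing schema implemented". Section 9 adds that "The SAP may modify what is outlined in the protocol where appropriate".

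**SAP.** The tertiary objective in Section 2.2 covers PK "following single dose(s) of a crystalline and SDD form of PF-07293893 in fasted and/or fed state". Section 6.3.2 still contemplates a formulation assessment, but provides this for it: "If the formulation and/or food effects are assessed, the PK parameters described in Section 3.3.2 will also be summarized descriptively". The model in that section has fasting condition as its only fixed effect, fasted as the reference, and "only data from the respective periods that includes the crystalline formulation will be included". Section 6.2 has a matching fed/fasted model for SDD, restricted to Cohort 3 periods. Section 5.2.3 and the key to Table 2 tie modelling to food effect alone. Section 2.1, on changes from the protocol's analysis plan, says "No modification".

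**The concern.** The SAP keeps the protocol's condition (formulation is assessed) but not the method that the protocol attaches to it. Someone who reads SAP 2.1 would expect the formulation model to stand, and would find otherwise only by comparing the analysis sections with Protocol 9.3.2.2.

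At stake is one exploratory output: an estimated crystalline/SDD ratio with its interval, using within-participant information where the same people receive both forms. Without a prespecified contrast, the reference, the SDD period to compare with and the handling of unequal doses would be settled after data have been seen, in a study where the sponsor is unblinded.

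**Working it through.** **1. Protocol and SAP side by side**

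| Element | Protocol 9.3.2.2 | SAP |
|---|---|---|
| Condition | formulation and/or food effect assessed | the same (6.3.2) |
| Outcomes | ln AUCinf, AUClast, Cmax | the same |
| Fixed effect | formulation and/or fasting condition | fasting condition only (6.2, 6.3.2) |
| Random effect | participant | participant |
| Data | not stated | SDD: Cohort 3 periods (6.2); crystalline: crystalline periods (6.3.2) |
| Test/reference | not stated | fed/fasted only |
| Interval | not stated | 90% CI, REML, Kenward-Roger (5.2.3, Appendix 2) |

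Neither SAP model contains both forms, so neither can yield a crystalline/SDD ratio. SAP 5.2 does treat each formulation and fasting status as a separate treatment, so the treatment term in Appendix 2 could carry formulation. But 5.2.3 restricts the model to food effect, and 6.2 and 6.3.2 each restrict it to one formulation. Most of the specification is already there. The contrast, its reference and the data subset are missing.

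**2. How many participants could contribute both forms**

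Protocol 9.5 plans 6 active and 2 placebo per dose level. For two periods of one cohort of 8, the overlap of active participants is at least 6 + 6 − 8 = 4 and at most 6. This assumes that all active participants of a period receive the same form. If the two forms go to different cohorts, the overlap is zero.

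**3. Precision of a 90% CI**

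The documents give no CVs, so all are assumed. With σ² = ln(1 + CV²), a within-participant (CVw) or between-participant (CVb) CV of 25% gives 0.0606; CVb 35% gives 0.1156 and CVb 50% gives 0.2231. The factor is the multiply/divide half-width on the ratio scale.

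- Six complete pairs, CVw 25%: SE = √(2 × 0.0606/6) = 0.1422; factor = exp(2.015 × 0.1422) = 1.33, whatever CVb is.
- Unpaired 6 v 6: SE = √(2 × (σw² + σb²)/6), t with 10 df = 1.812.
- Mixed model with 4 pairs plus 2 single-form participants per form: generalised least squares SE with variance σw² per observation and covariance σb² within a participant. The df are uncertain, so t is taken at 5 to 3 df (2.015 to 2.353).

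| CVw / CVb | Mixed model SE | Factor | Unpaired SE | Factor | SE ratio |
|---|---|---|---|---|---|
| 25% / 25% | 0.1557 | 1.37–1.44 | 0.2010 | 1.44 | 0.77 |
| 25% / 35% | 0.1608 | 1.38–1.46 | 0.2423 | 1.55 | 0.66 |
| 25% / 50% | 0.1655 | 1.40–1.48 | 0.3076 | 1.75 | 0.54 |
| 30% / 25% | 0.1825 | 1.44–1.54 | 0.2212 | 1.49 | 0.83 |

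The unpaired interval is only a yardstick; the SAP does not plan it. In the last row the model's range straddles the unpaired factor, so there is little or no gain.

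**The case against.** The strongest reply is that the protocol's wording offers formulation and/or fasting condition, sends details to the SAP and twice permits the SAP to modify. On that reading, a fasting-only model is one of the permitted choices, and the SAP makes that choice openly in four places. Much of this stands. A reader might infer a protocol breach; the documents do not support that, because the permission is explicit. What does not stand is the claim that nothing changed. The and/or follows what is assessed, SAP 6.3.2 still contemplates assessing formulation, and a modification that the protocol expects to be outlined is instead denied in 2.1.

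A second reply is that no objective goes unanalysed. This is correct. The listed endpoints are PK parameters, not a ratio. Geometric means by formulation, listings, profiles by participant and plots of dose-normalised parameters with individual values remain planned. A reader might infer that the formulation question is abandoned or that a primary or secondary result is weakened; neither follows.

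Third, the Figure 1 schema and the change letter of 14 Dec 2023 are not available. The SAP's change log cites the letter only for adding the SDD food effect, but whether it also altered the formulation plan cannot be checked.

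Finally, the contrast may be confounded with period, and dose normalisation is weak where absorption is dose-limited, as Protocol 2.2.4 anticipates. Both points stand and limit what the added analysis can show.

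**Conclusion.** The point holds as a minor one. The SAP narrows an optional, exploratory analysis by leaving out the formulation term, and its modification section does not say so. The protocol permits the narrowing, and primary and secondary results are untouched.

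Restoring the contrast answers the SDD-versus-crystalline question better than separate summaries, but only if some participants receive both forms in the same fasting state. A reader might infer a large loss of precision from its absence. That is not supported: every CV is assumed, and the gain over an unpaired comparison runs from clear (factor 1.40–1.48 against 1.75 at CVw 25%, CVb 50%) to little or none (1.44–1.54 against 1.49 at CVw 30%, CVb 25%). There is none if nobody receives both forms.

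**What to change.** In SAP 5.2.3, 6.3.2 and the Table 2 key, add a conditional rule:

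- If participants receive both crystalline and SDD in the same fasting state, fit the Appendix 2 model to ln AUCinf, ln AUClast and ln Cmax, with formulation as the treatment term, participant as random effect and SDD as the reference.
- Use the SDD period at the same dose. If there is none, use the SDD period with the nearest dose, dose-normalise, and label the result supportive.
- Report the crystalline/SDD geometric mean ratio with its 90% CI and the number of participants contributing both forms.
- Leave the crystalline-only food-effect model as it is.
- If no participant receives both forms, keep the comparison descriptive and declare that in SAP 2.1.

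The cost is a few sentences and one further application of the Appendix 2 code per parameter, with no new data. The downside is one more exploratory contrast, imprecise with about 4 to 6 pairs and possibly confounded with period. The report should state both limits beside the estimate.
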